2.1.6 Pharmacokinetics (PK) analysis set

The PK analysis set will include all subjects with at least one quantifiable AZD9567 concentration with a documented related dosing history. Subjects in the PK analysis set will be analysed according to their planned treatment arm, regardless of actual treatment received.

Subjects may be excluded from the PK analysis set if they have an adverse event (AE) of vomiting that occurs within approximately 2 times the median time of maximum observed drug concentration (t_{max}) or an important protocol deviation considered to affect PK. All decisions to exclude subjects from the PK analysis set will be made prior to the unblinding of the study.

2.2 Violations and deviations

2.2.1 Protocol deviation monitoring

During study conduct, protocol deviations will be closely monitored by the clinical team via the IMPACT report. A decision will be made prior to unblinding the study to determine which protocol deviations may significantly affect the study outcome and should result in a subject's exclusion from the PP or PK analysis sets.

The following categorisations of the protocol deviations will be used to identify important protocol deviations:

- Did not fulfil eligibility criteria.
- Received incorrect study treatment/dose.
- Received prohibited concomitant medication.
- Protocol-required procedure not adhered to.
- Developed discontinuation criteria but continued.

2.2.2 Protocol deviation reporting

Protocol deviations that may affect the study outcome significantly and the interpretability of the study results are defined as important protocol deviations (IPD).

The criteria for all important protocol deviations will be provided in a separate protocol deviation document from the SAP. Protocol deviations that the study team considers to be important will be tabulated or listed in CSR.

3. PRIMARY AND SECONDARY VARIABLES

3.1 Primary Variable

The difference in DAS28 units will be used to show that the efficacy of AZD9567 40 mg is equivalent to the efficacy of Prednisolone 20 mg at Day 15:

$$\text{Diff} = X_T - X_P$$

where X_T is the mean change from baseline in DAS28 of AZD9567 and X_P is the mean change from baseline in DAS28 of Prednisolone.

DAS28 scores will be derived at baseline and each post-baseline assessments using the following formula:

$$\begin{aligned} \text{DAS28 (CRP)} = & 0.56 * \sqrt{TJC28} + 0.28 * \sqrt{SJC28} + 0.014 * GH + 0.36 * \ln(CRP + 1) \\ & + 0.96 \end{aligned}$$

Where:

$TJC28$ = 28 joint count for tenderness (Section 3.1.1 [Tender Joint Counts](#)).

$SJC28$ = 28 joint count for swelling (Section 3.1.2 [Swollen Joint Counts](#)).

Global health (GH) = subject's global assessment on Visual Analogue Scale (VAS) of 100 mm (Section 3.1.3 [Global Health](#)).

$\ln(CRP)$ = natural logarithm of CRP (mg/L) (Section 3.1.4 [CRP](#)).

Refer to Section 4.4.1 Missing DAS28 (CRP) for handling of missing DAS28 (CRP) components.

The following supplementary variables will be used to calculate the primary variable DAS28:

3.1.1 Tender Joint Count 28

The following 28 joints (14 left, 14 right) will be evaluated for tenderness as obtained from the Joint Count Right or Left electronic case report form (eCRF):

- 2 each: Interphalangeal joints of the thumbs, wrist joints, elbow joints, shoulder joints, knee joints.
- 8 Proximal interphalangeal (PIP) joints of the fingers.
- 10 Metacarpophalangeal joints (MCP) joints.

The tender joint count represents the number of joints in which pain is reported after either manoeuvre.

$TJC28$ = Sum of tender joints with present status on the eCRF. Maximum $TJC28 = 28$.

Refer to Section 4.4.2 Missing tender or swollen joints for missing joint counts.

3.1.2 Swollen Joint Count 28

The same joints mentioned in Section 3.1.1 will be evaluated for swelling.

The swollen joint count represents the number of joints in which there is synovial fluid and or soft tissue swelling, but not if bony overgrowth is found.

SJC28 = Sum of swollen joints with present status on the eCRF. Maximum SJC28 = 28.

Refer to Section 4.4.2 Missing tender or swollen joints for missing joint counts.

3.1.3 Global Health

Subject's GH using patient's global assessment (PGA) of disease activity by means of the VAS.

The PGA VAS consists of a 100 mm long scale ranging for 0 (very well) to 100 (very poor). This VAS score is located on the subject's assessment of RA (SARA) eCRF.

3.1.4 C-reactive protein (CRP)

CRP (mg/L) is collected at the local laboratory for Visit 1. Central laboratory will be used for Visit 2, 4, 5 and 6. Visit 3 will be a phone call only, therefore no laboratory testing will take place on that visit.

3.2 Secondary Variables

There are 12 secondary efficacy variables in this study:

- Percentage of subjects achieving ACR20, ACR50 and ACR70 responses.
- Change from baseline in individual components of DAS28 and ACR response criteria:
 - SJC 66.
 - TJC 68.
 - SJC 28.
 - TJC28.
 - Subject's assessment of pain (VAS).
 - Subject's assessment of global disease activity (GH VAS).
 - Physician's assessment of global disease activity (VAS).
 - Subject's assessment of physical function.
 - CRP.

3.2.1 ACR20, ACR50 or ACR70

Subjects will be considered to have an ACR20, ACR50 or ACR70 response if a 20%, 50% or 70% improvement from baseline (respectively) occurred. The ACR20, ACR50 or ACR70 responses will be derived at each of the following post-baseline scheduled assessments:

- Day 8, Visit 4.
- Day 15, Visit 5.
- Day 28, Visit 6.

As Day 28, Visit 6 is a follow-up visit and two week off-treatment, a possible decrease in efficacy is expected.

A subject will have an ACR20 response if all of the following occur:

- A $\geq 20\%$ improvement in the SJC 66 (Section 3.2.2 [Swollen Joint count](#)).
- A $\geq 20\%$ improvement in the TJC 68 (Section 3.2.3 [Tender Joint count](#)).
- A $\geq 20\%$ improvement in at least 3 of the following 5 assessments:
 - Subject's assessment of pain:
Obtained from the VAS score on the Health Assessment Questionnaire (HAQ) eCRF.

- Subject's global assessment of disease activity (GH):
Obtained from the VAS score on the SARA eCRF.
- Physician's global assessment of disease activity:
Derived from the VAS score on the Investigator's Global Assessment of RA (IARA).
- Subject's assessment of physical function:
As derived by the Total score on the HAQ eCRF. See Appendix A Health assessment questionnaire score derivation for more information.
- Acute phase reactant (CRP measure in mg/L).

A subject will have ACR50 or ACR70 response if a 50% or 70% improvement from baseline (respectively) rather than 20% was observed in the criteria specified above for ACR20.

Refer to Section 4.4.3 Missing ACRxx components for missing ACR components.

3.2.2 Swollen Joint count 66

The following 66 joints (33 left, 33 right) will be evaluated for swelling:

- 2 each: Temporomandibular, sternoclavicular, acromioclavicular, interphalangeal joints of the thumbs, wrist joints, elbow joints, shoulder joints, knee joints, ankle mortise and tarsus.
- 8 each: PIP joints of the fingers, distal interphalangeal joints.
- 10 each: Metatarsophalangeal, MCP joints, toe joints.

The swollen joint count represents the number of joints in which there is synovial fluid and/or soft tissue swelling, but not if bony overgrowth is found.

SJC = Sum of swollen joints with present status on eCRF. Maximum SJC = 66.

Refer to Section 4.4.2 Missing tender or swollen joints for missing joint counts.

3.2.3 Tender Joint count 68

The following 68 joints (34 left, 34 right) will be evaluated for swelling:

- 2 each: Temporomandibular, sternoclavicular, acromioclavicular, interphalangeal joints of the thumbs, wrist joints, elbow joints, shoulder joints, knee joints, hip joints, ankle mortise and tarsus.

- 8 each: PIP joints of the fingers, distal interphalangeal joints.
- 10 each: Metatarsophalangeal, MCP joints, toe joints.

TJC = Sum of tender joints with present status on eCRF. Maximum TJC = 68.

Refer to Section 4.4.2 Missing tender or swollen joints for missing joint counts.

3.2.4 Change from baseline in individual components of DAS28

The four individual components of DAS28 (as discussed in Primary Variables Section 3.1: TJC 28, SJC 28, subject's global assessment of disease activity [GH], CRP) will be used in order to calculate change from baseline.

3.2.5 Change from baseline in individual components of ACR

The seven individual components of ACR (as discussed in Section 3.2.1: SJC 66, TJC 68, subject's assessment of pain, subject's global assessment of disease activity [GH], physician's global assessment of disease activity, subject's assessment of physical function, CRP) will be used in order to calculate change from baseline. Appendix A Health assessment questionnaire score derivation

3.3 Pharmacokinetics

The derivation of the PK parameters for AZD9567 will be performed at Covance (Clinical Pharmacology Alliance). The PK parameters will be derived using non-compartmental methods with Phoenix WinNonlin (Version 8.1 or higher).

The PK profile of AZD9567 in subjects with active RA in spite of stable treatment with conventional and/or s.c./i.v. biological DMARDs will be assessed by calculating the following parameters where possible:

AUC(0-24): Area under the plasma concentration-time curve from time zero to 24 hours after study treatment dose.

AUC(last): Area under the plasma concentration-time curve until the last quantifiable concentration

AUC(0-6): Area under the plasma concentration-time curve from time zero to 6 hours after study treatment dose.

tmax: Time point of the maximal plasma concentration of a drug.

Cmax: Maximum observed drug concentration.

Ctrough: The last plasma concentration measured before the last dose.

CL/F: Apparent plasma clearance following an extravascular dose.

Vz/F: Apparent volume of distribution following an extravascular dose.

Other pharmacokinetic parameters may be calculated if appropriate.

The following diagnostic parameters for plasma PK analysis may be listed but will not summarised:

λ_z : Terminal elimination rate constant

$\lambda_z N$: Number of data points included in the log-linear regression analysis

Rsq_adj: Regression coefficient adjusted for n obs, Goodness of fit statistic for the calculation of λ_z

AUCextr(0-24): Percentage of AUC(0-24) obtained by extrapolating the area under the plasma concentration-time curve from the time of the last quantifiable concentration to 24h. Pharmacokinetic analysis will, where possible times recorded in the raw data. If actual times are missing, nominal times may be used.

Concentrations are used as supplied by the analytical laboratory for PK analysis. The units of concentration and resulting PK parameters, with amount or concentration in the unit, will be presented as they are received from the analytical laboratory

Cmax and tmax will be obtained directly from the plasma concentration-time profiles. For multiple peaks, the highest post-dose concentration will be reported as Cmax. In the case that multiple peaks are of equal magnitude, the earliest tmax will be reported.

Concentrations below the limit of quantification (BLQ) from the time of pre-dose sampling ($t=0$) up to the time of the first quantifiable concentration will be set to zero with the following exceptions:

- Any embedded BLQ value (between 2 quantifiable concentrations) and BLQ values following the last quantifiable concentration in a profile will be set to missing for the purposes of PK analysis.
- If there are late positive concentration values following 2 BLQ concentration values in the apparent terminal phase, these values will set to missing unless there is a scientific rationale not to do so, which will be documented by the pharmacokineticist.
- If an entire concentration-time profile is BLQ, the profile will be excluded from the PK analysis.
- If a pre-dose concentration is missing, these values may be set to zero by default.

The terminal elimination half-life, calculated as $(\ln 2/\lambda_z)$ will be estimated by log-linear least squares regression of the terminal phase of the concentration-time curve. The choice of data points used to estimate λ_z should follow the general guidelines:

- The start of the terminal elimination phase for each subject will be defined by visual inspection and will be the first point at which there is no systemic deviation from the log-linear decline in plasma concentrations.
- A minimum of 3 data points will be used in calculating λ_z and the duration of time over which λ_z is recommended to be at least 3 times the subsequently estimated terminal half-life. Where the elimination half-life is estimated over less than 3 times the subsequently estimated terminal half-life it will be flagged in the data listings and discussed in the study report.
- Should include the last measurable concentration
- Include only observations after Cmax
- The λ_z may not be assigned if the R^2 adjusted value of the regression line is less than 0.8. In cases where the λ_z is not assigned all regression-based parameters (including R^2 adjusted) will not be calculated

AUCs will be calculated using the linear trapezoidal method when concentrations are increasing and the logarithmic trapezoidal rule when concentrations are decreasing (linear up log down). The minimum requirement for the calculation of AUC will be the inclusion of at least 3 consecutive plasma concentrations above the LLOQ.

AUC(0-24) values where the percentage extrapolation is $<20\%$ will be reported. AUC(0-24) values where the percentage extrapolation is $\geq 20\%$ will be flagged.

If a value is considered to be anomalous due to being inconsistent with the expected PK profile, it may be appropriate to exclude this point from the PK analysis. However, the exclusion of data must have strong justification and will be documented in the raw data and the CSR.

PK parameter data associated with quantifiable pre-dose values $>5\%$ of Cmax may be excluded from the summary statistics and statistical analysis at the discretion of the Pharmacokineticist.

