4. STUDY PLAN AND TIMING OF PROCEDURES

Table 1 Study Plan detailing the procedures

Study procedures	Screening Visit 1	Day 1 Visit 2 (within 1 week of V1)	Day 5 Phone call Visit 3	Day 8 +/- 1 Visit 4	Day 15 +/- 1 EOT ^a Visit 5	Day 28 +/- 2 Follow-up Visit 6
Inclusion/exclusion criteria	X					
Demographic data	X					
Medical history (incl. RA history and oral health)	X					
Concomitant medication	X	X	X	X	X	X
Informed consent	X					
Informed consent for genetic sample	X					
Randomisation		X				
Study drug dispensation		X ^b		X		
Study drug administration:		X ^b	→	→ NB: at site	X NB: at site	
Study drug return					X	
Adverse events		X	→	→	→	X
Serious adverse events	X	→	→	→	→	X
Vital signs (BP/P and body temperature)	X	X ^d		X	X	X
12-lead ECG	X	X ^{d, f}			X	X
Clinical laboratory evaluations (Haematology, serum biochemistry, endocrinology ^e , and urine ^e analysis)	X ^c	X ^d		X ^d	X ^d	X
Pregnancy test (serum)	X					X
Erythrocyte sedimentation rate, ESR (at site)	X	X ^d		X ^d	X ^d	X
Physical examination,	X	X		X	X	X
Body weight & height ^e	X				X	X
DAS28-CRP	X	X ^d		X	X	X
ACR20, 50, and 70	X	X ^d		X	X	X
SJC and TJC 66/68	X	X ^d		X	X	X
Blood sampling for exploratory biomarkers (cortisol, serum)		X ^{d,g} Profile: 0, 1, 2, 3, 4 and 6 h			Pre dose ^g & 1, 2, 3, 4 and 6 h post dose	
Blood sampling for exploratory biomarkers (LPS stimulated TNF α , whole blood)		X ^d Profile: 0, 1, 2, 3, 4 and 6 h			Pre dose & 1, 2, 3, 4 and 6 h post dose	
Blood sample (whole blood) for mRNA ⁱ		X ^d			X ^h	

Table 1 Study Plan detailing the procedures

Study procedures	Screening Visit 1	Day 1 Visit 2 (within 1 week of V1)	Day 5 Phone call Visit 3	Day 8 +/- 1 Visit 4	Day 15 +/- 1 EOT ^a Visit 5	Day 28 +/- 2 Follow-up Visit 6
Blood sample for other potential biomarkers (serum)		X ^d			X ^d	X
Blood sample for DNA (future exploratory research)		X ^b				
Blood sampling for PK of AZD9567/ prednisolone					Pre-dose, 0.25, 0.5, 1, 1.5, 2, 3, 4 and 6 h	

^a End of treatment

^b After randomisation

^c Local lab

^d Pre-dose

^e Only at Visit 1

^f Only performed if Visit 1 was >3 days ago

^g Preferably starting as close to 08.00 as possible

^h At 1h post dose (C_{max})

ⁱ A peripheral blood mononuclear cell method may be used at selective site/s

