8.5.2.1 Pharmacokinetic analyses

The derivation of the PK parameters will be performed at Covance (Clinical Pharmacokinetic Alliance). The PK parameters will be derived using non-compartmental methods with Phoenix® WinNonlin® Version 6.3, or higher (Pharsight Corp., Mountain View, California), in accordance with “Best Practice Reference Guidelines Pharmacokinetic Evaluations in Clinical Studies”. All descriptive statistical computations will be performed using SAS Version 9.2, or higher.

Where possible, the following PK parameters will be assessed for AZD9567 and prednisolone.

$AUC_{(0-24)}$	Area under the plasma concentration-time curve from time zero to 24 hours after administration (using the pre-dose value as the 24 h time point)
$AUC_{(0-\text{last})}$	Area under the plasma concentration-time curve from time zero to the time of the last quantifiable concentration
$AUC_{(0-6)}$	Area under the plasma concentration-time curve from time zero to 6 h after administration
t_{\max}	Time to reach maximum plasma concentration
C_{\min}	Predose concentration

Additional PK parameters may be determined where appropriate.

Further details regarding the calculation and descriptive statistics of the PK parameters will be described in the SAP.

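### AZD9567 sampling ends at 6 h, so the recommended lambda-z window is met only if the half-life is about 1.5 h or less, and nothing keeps under-spanned Vz/F (and t1/2z, if summarised) out of the summaries

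*SAP*

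**What the plan says.** Protocol Table 1 schedules AZD9567 sampling at Visit 5 only: "Pre-dose, 0.25, 0.5, 1, 1.5, 2, 3, 4 and 6 h". A footnote to the same table, attached to the mRNA sample, places Cmax "At 1h post dose".

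SAP 3.3 sets guidelines for lambda-z:
- "A minimum of 3 data points will be used in calculating" lambda-z;
- "Include only observations after Cmax";
- the regression span "is recommended to be at least 3 times the subsequently estimated terminal half-life";
- if the span is shorter, "it will be flagged in the data listings and discussed in the study report";
- lambda-z may be left unassigned when adjusted R² is below 0.8, and then no regression-based parameter is calculated.

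The same section names Vz/F ("Apparent volume of distribution following an extravascular dose") as a parameter, and SAP 4.3.3.4 summarises the parameters listed in 3.3. The half-life is less clear. It is defined in the text of 3.3 but missing from that section's parameter list, while 4.3.3.4 gives number formats for its descriptive statistics. Lambda-z itself is for listing only in 3.3, yet 4.3.3.4 formats its descriptive statistics too.

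For AUC(0-24), Protocol 8.5.2.1 specifies "using the pre-dose value as the 24 h time point". SAP 3.3 instead describes the part beyond the last quantifiable concentration as extrapolated to 24 h. The table of changes in SAP section 6 does not list this difference.

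**The concern.** A slope fitted between about 1.5 and 6 h describes terminal elimination only if the terminal phase has begun by then and the concentration falls enough over the window to fix the slope. If not, the half-life comes out too short or poorly determined. Vz/F carries the same error, because it is CL/F divided by lambda-z.

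The SAP foresees short windows, but its response is a flag in the listings and a discussion. It does not say whether flagged values enter the means and geometric means, so the printed summary could consist almost wholly of flagged values.

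The pharmacokinetic profile of AZD9567 in patients is a secondary objective, and Protocol 4.2 says that 5 days was the longest previous treatment. The AUC(0-24) inconsistency matters more directly, because that parameter is named in the objective. If lambda-z drives the extrapolation, which the SAP does not state, its error also enters AUC(0-24) and any CL/F based on it.

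**Working it through.** **Inputs.** Sampling times and tmax of about 1 h come from Protocol Table 1. The span, minimum-points and R² criteria come from SAP 3.3. The documents give no half-life, assay error or number of phases, so these are assumptions: half-lives of 1.5 to 8 h, and log-scale error of 0.10 unless stated. The plan gives no figure of its own to reproduce.

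**1. Longest half-life that meets the recommendation** = (6 − first sample after tmax) / 3.

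| tmax (h) | First usable sample (h) | Span (h) | Longest half-life (h) |
|---|---|---|---|
| 0.25 | 0.5 | 5.5 | 1.83 |
| 0.5 | 1 | 5.0 | 1.67 |
| 1 | 1.5 | 4.5 | 1.50 |
| 1.5 | 2 | 4.0 | 1.33 |
| 2 | 3 | 3.0 | 1.00 |

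With tmax at 3 h or later, fewer than three samples remain and lambda-z cannot be estimated. For the 4.5 h span, span divided by half-life is 1.5 at 3 h, 0.9 at 5 h and 0.56 at 8 h, against the recommended 3.

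**2. Precision.** For samples at 1.5, 2, 3, 4 and 6 h the mean time is 3.3 h and Sxx = 3.24 + 1.69 + 0.09 + 0.49 + 7.29 = 12.8. For a single-phase decline, CV(lambda-z) = error × half-life / (ln 2 × √12.8):
- 3 h: 0.10 × 3 / (0.693 × 3.578) = 12%
- 5 h: 0.10 × 5 / 2.480 = 20%
- 8 h: 0.10 × 8 / 2.480 = 32%

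At an error of 0.20 these double.

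**3. Effect of the adjusted R² ≥ 0.8 filter** (simulation, five samples, error 0.10).

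| Assumed true decline | Profiles passing | Median half-life of those passing (h) |
|---|---|---|
| Single phase, 3 h | 99% | 2.99 |
| Single phase, 4 h | 89% | 3.94 |
| Single phase, 6 h | 59% | 5.55 |
| One compartment, 8 h | 36% | 6.9 |
| Two phases, 1.5 h and 8 h (70/30) | 97% | 3.1 |

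The 5th to 95th percentiles of retained values are 2.50 to 3.72 h in the 3 h case and 4.9 to 11.2 h in the 8 h case. At an error of 0.20 the trouble starts earlier: with a true 4 h, 37% pass and their median is 3.4 h.

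In the two-phase case, starting the fit later by visual inspection helps little. Error-free fits starting at 1.5, 2 and 3 h give 3.08, 3.22 and 3.48 h against a true 8 h.

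Vz/F = (CL/F) × half-life / ln 2. For a given CL/F, the two-phase case therefore returns 3.1 / 8 = 0.39 of the true Vz/F, and the one-compartment 8 h case 6.9 / 8 = 0.86.

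**4. Reach into AUC(0-24).** In a one-compartment steady-state model with tmax 1 h, the share of AUC(0-24) beyond 6 h is 8% at a half-life of 1.5 h, 15% at 2 h, 27% at 3 h and 48% at 6 h. The SAP's 20% flag would be reached at roughly 2.4 h.

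**5. Pre-dose value as a 24 h point.** The longest half-life meeting the recommendation becomes (24 − 1.5) / 3 = 7.5 h, or (24 − 4) / 3 = 6.7 h if the fit uses 4, 6 and 24 h. With that three-point fit, the 5th to 95th percentiles in the one-compartment 8 h case are 7.1 to 9.1 h, and the two-phase median is 6.7 h. Adjusted R² passes in every simulated profile.

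**6. The 5% pre-dose criterion.** SAP 3.3 also lets the pharmacokineticist exclude parameters from summaries when pre-dose exceeds 5% of Cmax. In the model of step 4, trough over Cmax is 0.003% at 1.5 h, 0.54% at 3 h, 4.3% at 5 h and 13.9% at 8 h. The 5% line is crossed at about 5.3 h.

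**The case against.** A reader might infer that the plan breaks a binding rule of its own. It does not. The three-half-life span is a recommendation among general guidelines, shortfalls are foreseen, and parameters are derived only where possible.

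A reader might also infer that the reported half-lives will certainly be wrong. The documents do not support that, since they give neither a half-life nor the shape of the decline. With one phase, a half-life of 1.5 to 3 h and 10% error, the estimates would be flagged but sound, with a CV of at most 12% and negligible bias.

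Nor is flagging the only safeguard. The R² filter removes many poor fits, so a spread taken from unfiltered three-point fits would overstate what the SAP would report. The 5% pre-dose criterion could remove long-half-life subjects as well.

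These points limit the concern but do not remove it. The R² filter tests straightness, not whether the right phase was fitted, so it passes nearly all of the two-phase profiles. For a single long phase it keeps the steeper slopes and so biases the remainder low. The 5% criterion is discretionary and would tend to remove exactly the subjects with long half-lives.

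It is also fair that Vz/F and t1/2z are absent from the stated secondary objective, and that whether t1/2z is summarised is unclear. The documents do not say that either will inform later dosing decisions, so no such consequence is claimed here.

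**Conclusion.** The point holds conditionally. The ceiling of about 1.5 h follows from the documents once tmax is taken as about 1 h. Above it most subjects will be flagged, and the SAP does not say that flagged Vz/F, or t1/2z if summarised, stays out of the summaries.

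How much harm follows depends on facts that the documents do not give. There is little for a single phase up to about 3 h with 10% error. From roughly 5 h the main problem is imprecision, with low bias growing as the half-life lengthens. In the assumed two-phase case the half-life is understated by more than half, with almost no warning from the fit statistic.

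The differing AUC(0-24) conventions in protocol and SAP are a plain inconsistency that needs reconciling whatever the half-life. All of this is secondary pharmacokinetics.

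**What to change.** Amend SAP 3.3 and 4.3.3.4:

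1. At Visit 5, use the measured, quantifiable pre-dose concentration as the 24 h value for AUC(0-24), restoring the protocol's convention. Where the previous dose is documented, also use it as a late point in the lambda-z regression, stated as an exception to the after-Cmax guideline. A missing pre-dose value set to zero, which SAP 3.3 allows, should not serve as a 24 h value.
2. List lambda-z, t1/2z and Vz/F, but leave them out of summary statistics when the span is below three estimated half-lives. With a 24 h point this admits half-lives only up to about 6.7 to 7.5 h, so nearly all subjects in an 8 h case would be listed only. Inspect each fit visually, because a single 24 h point dominates R². Make the parameter list in 3.3 agree with the formats in 4.3.3.4.
3. State that the 5% pre-dose criterion is not used to drop steady-state profiles with a genuine trough.
4. If the sponsor does not want the 24 h point in the regression, list t1/2z and Vz/F only. Continue to summarise Cmax, tmax, AUC(0-6), AUC(last), AUC(0-24), Ctrough and CL/F, with AUC(0-24) and CL/F based on the protocol's pre-dose convention.

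The cost is SAP wording and one data-handling step, with no extra sample, visit or patient. The downside is reliance on steady state and a correctly timed previous dose, and fewer subjects with a summarised half-life.

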1.3 Number of subjects

It is planned to randomise approximately 40 subjects in total, 20 subjects to each treatment group. It is anticipated that approximately 80-100 subjects will need to be screened in order to achieve randomisation total. Planned recruitment of subjects will take place across 7 sites in 2 countries (Sweden and Netherlands).

The main analysis will be based on the difference in the mean CFB for AZD9567 and the mean CFB of prednisolone.

The details of the sample size calculation are based on internal decision criteria as explained in Frewer et al, 2016. In these calculations we use the reliability threshold of the DAS28 index known to be 0.6 (Siemons et al, 2014).

A sample size of n=10 per group was agreed on however is not sufficiently powered to support hypothesis testing.

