- tmax, t lower and t upper time limit – will be presented as received in the data, usually to 2 decimal places
- AUClast, t_{1/2}Z, CL/F, Vz/F, Rsq adj will be presented to 3 significant figures
- λz – will be presented to 4 significant figures
- λz, N – will be presented as an integer (no decimals)
- AUC(0-24)extr – will be presented to 2 decimal places

For PK concentration data all descriptive statistics will be presented to 4 significant figures with the exception of the minimum and maximum which will be presented to 3 significant figures.

For PK parameters data the descriptive statistics will be presented according to the following rules:

- Cmax, AUClast, t_{1/2}Z, CL/F, Vz/F – all descriptive statistics will be presented to 4 significant figures with the exception of the minimum and maximum which will be presented to 3 significant figures
- λz – all descriptive statistics will be presented to 5 significant figures with the exception of the minimum and maximum which will be presented to 3 significant figures
- tmax – all descriptive statistics will be presented as received in the data, usually to 2 decimal places

Individual plasma concentrations of AZD9567 will be plotted for each subject based on actual timepoint the sample was collected in linear and semi-logarithmic scale. NQ results will be plotted as the LLOQ for the linear scale and log(LLOQ) for the semi-logarithmic scale.

The geometric mean (+/-GSD) plasma concentrations of AZD9567 will be plotted by planned timepoint in linear and semi-logarithmic scale (no GSD bars). For mean plots, BLQ values will be handled as described for the summary tabulations; for individual plots plasma concentrations which are <LLOQ prior to the first quantifiable concentration will be set to a value of zero (linear plots only). After the first quantifiable concentration, any <LLOQ plasma concentrations will be regarded as missing.

Pharmacokinetic parameters will be listed.

A listing of plasma concentrations of AZD9567 including sample collection times as well as derived sampling time deviations will be provided.

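### SAP 3.3 lets PK parameter data be dropped when the pre-dose value exceeds 5% of Cmax, but at Visit 5 that value is an expected trough; the 24 h method for AUC(0-24) also needs one clear statement

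*SAP*

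**What the plan says.** **Sampling.** Protocol Table 1 schedules PK blood samples only at Visit 5: pre-dose and eight times up to 6 h after the dose. Protocol 7.2 has that day's dose taken at the site so that the pre-dose sample can be drawn. Dosing is once daily from Visit 2, and no washout is planned before Visit 5.

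**The pre-dose value is a planned result.** SAP 3.3 lists "Ctrough: The last plasma concentration measured before the last dose" among the parameters to be derived.

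**The exclusion rule.** The same section allows parameter data with a quantifiable pre-dose value above 5% "of Cmax may be excluded from the summary statistics and statistical analysis at the discretion of the Pharmacokineticist". It gives no further criterion.

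**Nearby safeguards.** For values judged anomalous against the expected profile, SAP 3.3 says that "the exclusion of data must have strong justification and will be documented in the raw data and the CSR". SAP 2.1.6 says "All decisions to exclude subjects from the PK analysis set will be made prior to the unblinding of the study". SAP 4.3.3.4 says "Pharmacokinetic parameters will be listed".

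**AUC(0-24).** Protocol 8.5.2.1 takes the pre-dose concentration as the value at 24 h. SAP 3.3 defines AUC(0-24) without that instruction. It adds a diagnostic, the percentage of AUC(0-24) "obtained by extrapolating the area under the plasma concentration-time curve from the time of the last quantifiable concentration to 24h", and flags values of 20% or more. The table of changes in SAP Section 6 has no PK entry. SAP 3.3 also permits a missing pre-dose concentration to be set to zero.

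**The concern.** A limit on pre-dose concentration relative to Cmax makes sense where no drug should be present before the dose. Here drug is expected. The SAP therefore measures the trough as a result and also treats a sizeable trough as a ground for removing the subject's parameters.

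The trigger is a trough-to-peak ratio, so any exclusions would not be random: slow eliminators go first and the largest Ctrough values are lost. AUC would be summarised too low and CL/F too high, but only so far as half-life varies between subjects through clearance. The SAP states that "A sample size of n=10 per group was agreed on", so two exclusions would remove a fifth of the AZD9567 data.

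The 24 h question matters because sampling stops at 6 h. A large part of AUC(0-24) then depends on how the remaining 18 h are filled in, and the reader cannot tell from the SAP which method will be used.

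**Working it through.** **1. Is there only one profile?** Table 1 gives pre-dose plus 0.25, 0.5, 1, 1.5, 2, 3, 4 and 6 h, which is 9 samples. At 3 mL each that is 27 mL. Protocol Table 3 states 9 PK samples and 27 mL, so the figures agree and there is a single profile, after repeated dosing.

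**2. When does an ordinary trough exceed 5% of Cmax?** The documents give no half-life, so it is varied. The model is one-compartment at steady state with a 24 h interval and k = ln 2 / half-life:

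C(t) = ka/(ka − k) × [e^(−kt)/(1 − e^(−24k)) − e^(−ka·t)/(1 − e^(−24ka))]

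A footnote to Table 1 places Cmax at about 1 h. With ka = 3 per h, the modelled peak falls at 0.9 to 1.1 h for half-lives of 3 to 6 h, so ka = 3 is the main case. For a half-life of 4 h, k = 0.1733:
- C(0) = 1.0613 × (1/0.98438 − 1) = 0.0168
- C(1) = 1.0613 × (0.8409/0.98438 − 0.0498) = 0.854
- Ratio = 0.0168/0.854 = 2.0%

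The same ratio at half-lives of 3, 5, 6 and 8 h is 0.5%, 4.4%, 7.4% and 14.3%. Setting it to 5% gives a half-life of 5.22 h. Over ka 1 to 5 the trigger lies between 4.8 and 5.3 h.

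**3. How many would go if the rule were always applied?** Assume lognormal half-lives with a CV of 30%, so σ = √ln(1.09) = 0.2936. With median 4 h and ka = 3:
- z = ln(5.22/4)/0.2936 = 0.91
- Share excluded = 1 − Φ(0.91) = 18%, or about 1.8 of 10

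**4. What happens to AUC?** AUC = dose/CL.
- If half-life varies only through volume, selecting on half-life leaves geometric mean AUC unchanged: 0% low.
- If it varies only through clearance, the shift in mean log AUC is −σ·φ(z)/Φ(z) = −0.2936 × 0.264/0.818 = −0.095. Since e^(−0.095) = 0.91, AUC is about 9% low, and CL/F is about 10% high (1/0.91).
- If clearance explains half of the log-variance, the shift is half as large: about 5% low.

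Range at ka = 3:

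| Median half-life | Excluded | AUC low, clearance only |
|---|---|---|
| 3 h | 3% | 2% |
| 4 h | 18% | 9% |
| 5 h | 44% | 19% |
| 6 h | 68% | 28% |

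**5. How much of AUC(0-24) lies after the last sample?** Integrating the model gives, at ka 1.5 to 3, 27–29%, 36–39%, 43–46% and 49–51% after 6 h for half-lives of 3, 4, 5 and 6 h. If extrapolation were the method, every one of these would exceed the 20% flag.

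**6. Does the choice of method change the answer?** With one exponential phase and no measurement error the two methods agree. With two phases (assumed half-lives 2 h and 8 h, slow share f = 5%, 10% and 20%, no absorption phase), each phase is superposed daily: (1 − f)·e^(−at)/(1 − e^(−24a)) + f·e^(−bt)/(1 − e^(−24b)). The methods then give, relative to the true AUC(0-24):
- Pre-dose as the 24 h value, log-linear from 6 h: 1.064, 1.064, 1.053
- Extrapolation on the slope of the 3, 4 and 6 h samples: 0.955, 0.926, 0.896

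With an absorption phase (ka = 3) the ranges are about 5 to 7% high and 5 to 11% low.

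**The case against.** The rule is permissive. By planning a Visit 5 pre-dose sample and Ctrough, the authors show that they expect a trough, so a competent pharmacokineticist may never invoke it. A reader might infer that the planned summaries will be biased; the documents do not support that, because nothing says the rule will be used.

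Unnoticed selective loss also needs a mid-range half-life. At a median of 3 h almost nobody is dropped. At 8 h about 93% would be (same model, ka = 3), and the near-empty table would be obvious. The demand for strong justification can be read as covering every exclusion, and the listings would let a reader trace what was left out. The PK summaries are descriptive and of one drug, so the timing of decisions relative to unblinding matters little.

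On AUC(0-24), a reader might infer that the SAP has replaced the protocol's method. That is not established. The SAP's definition is otherwise the same, the protocol leaves further detail to the SAP, and the diagnostic can be read simply as the share after the last sample. On a missing pre-dose value, SAP 4.3.3.4 already leaves absent results out of the statistics, and Ctrough is defined as a measured value.

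These points limit the weight of the concern. They do not remove it: the justification sentence opens with anomalous points, the pre-unblinding sentence concerns membership of the PK analysis set, and neither is clearly written for the 5% rule. Listings make an exclusion traceable but do not prevent it.

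**Conclusion.** The exclusion rule does not suit the only profile to which it can apply. Used as written, it would remove valid data from slow eliminators. Its size cannot be fixed from the documents: it is zero if the rule is unused. In the conditional example it is about 18% of subjects, with geometric mean AUC 0 to 9% low. That rests on one-compartment steady state, ka = 3, a median half-life of 4 h and a CV of 30%.

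The AUC(0-24) point is an unreconciled difference in wording, and the SAP may be silent rather than changed. AZD9567 PK is a secondary objective with no test or decision rule, so this is a low-priority improvement that the sponsor could make.

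**What to change.** In SAP 3.3:

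1. State that the exclusion for pre-dose values above 5% of Cmax does not apply to the Visit 5 profile except for documented dosing or sampling errors. Show summaries with and without any subject so excluded.
2. State one method for AUC(0-24). Keeping the protocol's method when the recorded previous dose was about 24 h earlier is reasonable. If extrapolation is intended instead, record and justify it in SAP Section 6.
3. Add that a missing pre-dose value is never carried to 24 h as zero.

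The cost is three sentences and a setting in the non-compartmental analysis, with no new samples. The protocol's method has its own price. It assumes a stable trough and needs the time of the previous dose. A true interval of 22 h or 28 h would shift AUC(0-24) by about +3 to +4% or −5 to −7% (half-life 3 to 8 h, ka 2). Under two-phase decline it reads somewhat high, as shown in the working, though by no more than extrapolation reads low once the slow phase is appreciable.
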